- Official title: The effect of warm saline irrigation on the amount of bleeding in impacted mandibular third molar surgery: a split-mouth double-blinded randomized clinical trial
- NCT number: NCT04143373
- Document date: November 1, 2019

Study Protocol and Statistical Analysis Plan

To meet the objectives of this split-mouth double-blinded randomized controlled clinical trial, 20 patients who were candidates for bilateral surgical extractions of mandibular third molars were chosen. The participants were selected based on their attendance in the Department of Oral and Maxillofacial Surgery of Tehran University of Medical Sciences, Tehran, Iran from October to December 2017. The sample size was defined to obtain test powers greater than 95% ($\alpha = 0.05$, $\beta < 0.05$).

Patients were enrolled in this study voluntarily, and the details on the study design were explained to them prior to signing the informed consent agreement. The study design was approved by the Institutional Review Board of Tehran University of Medical Sciences, according to the principles of the Helsinki declaration (thesis #6234) and was registered in <https://clinicaltrials.gov> (Code: NCT04143373).

The Inclusion and Exclusion criteria were defined as follows:

Inclusion criteria

- Being a candidate for bilateral mandibular third molar surgery
- Both mandibular third molars must have a similar inclination to the second molar
- Both mandibular third molars must have same Pell & Gregory's classification, indicating the similar surgical difficulty on both sides.

Exclusion criteria

- Presence of any systemic condition or using any type of medication

- History of allergy to local anesthetic (LA) solutions
- Patients with an active gag reflex, because they are more susceptible to swallow the irrigation solution.
- Pregnant and post-menopause women
- Patients with pericoronitis or any local inflammation

Since it is easier and less time-consuming for the right-handed surgeon to extract the impacted molar on the right side, all surgeries were performed by one right-handed oral and maxillofacial surgeon. For each patient, the control and the experimental sides were chosen by a table of random numbers. The surgeon was aware of the experimental side, however the outcome assessor who checked the amount of suctioned solution, and the data analyst were blind. In the control side and the experimental side, $25\pm2^{\circ}\text{C}$ and $37\pm1^{\circ}\text{C}$ saline were used for irrigation, respectively. All other variables such as the flap type, number, and type of LA cartridges and suturing method were matched between both sides in each patient.

The total time needed for surgery was measured from the moment of the LA injection until the end of suturing. For each patient only 2 cartridges of lidocaine 2% along with 1:100000 epinephrine were used to block the inferior alveolar (direct technique), lingual and long buccal nerves. The timespan between LA injection and the start of surgery was relatively the same. In case the surgery on one side took a relatively longer time, that case would have been excluded.

The amount of saline for irrigation was precisely measured and patients were asked to prevent swallowing till the end of surgery so that all the solutions and debris were suctioned from the oral cavity. In case the volume of irrigation solution was different between control and experimental sides, compensative amount of saline was poured into the mouth and suctioned to balance the amount of suctioned solutions. Also, it was presumed that in healthy patients who were not on any medications, salivary secretion rates were almost the same between surgeries, so that the difference between the volumes of suctioned solutions were due to the differences in bleeding.

The SPSS (Version 23.0, IBM Corp., 2015, New York, USA) and Independent sample T-test were used to analyze the findings.

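### Does the claim of more than 95% power with 20 patients need to be corrected?

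*Combined protocol and SAP*

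**What the plan says.** The opening paragraph of the combined protocol and SAP reports that "20 patients who were candidates for bilateral surgical extractions of mandibular third molars were chosen". On the number it says only "The sample size was defined to obtain test powers greater than 95" per cent, with alpha 0.05 and beta below 0.05. It names no target difference, SD, correlation between the two sides of a mouth, sidedness or formula.

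Three later statements bear on that figure:

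- **Design** (paragraph on the surgeon and allocation): "For each patient, the control and the experimental sides were chosen by a table of random numbers". The data are therefore 20 pairs.
- **Exclusions** (paragraph on surgery time): "In case the surgery on one side took a relatively longer time, that case would have been excluded". There is no numerical threshold, no expected number of exclusions and no stated inflation of the sample size.
- **Analysis** (last sentence): "Independent sample T-test were used to analyze the findings".

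**The concern.** Power belongs to a sample size, a test and an effect taken together. Quoted for the sample size alone, a figure above 95% reads as a general property of the trial, and a reader might then take a null result as strong evidence that warm saline makes no difference.

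Two features of the plan add to the doubt. If 20 was derived for a paired test, the independent test named for the analysis would have less power whenever the two sides are positively correlated. And if 20 pairs were only just enough, any case excluded for unequal surgery time would bring the trial below its stated power.

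**Working it through.** **The plan's own figure.** It cannot be reproduced, because the effect, SD, correlation and sidedness are missing. The check therefore runs in reverse and asks what difference would make the statement true.

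**Inputs from the document.** 20 patients, hence 20 sides per condition or 20 pairs; alpha 0.05; power above 0.95; independent t-test.

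**Assumptions.** Two-sided testing unless noted; equal SD on both sides; within-patient correlation ρ from 0 to 0.9. Let d be the mean difference divided by the between-patient SD, and dz the mean difference divided by the SD of the within-patient differences, so that d = dz × √(2(1 − ρ)).

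**Step 1: independent t-test, ρ = 0.** Power is the upper tail of a noncentral t with 38 df and noncentrality d × √(20/2) = 3.162d.

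| d | 0.5 | 0.8 | 1.0 | 1.17 | 1.2 | 1.5 |
|---|---|---|---|---|---|---|
| Power | 33.8% | 69.3% | 86.9% | 95.0% | 95.9% | 99.6% |

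The 95% point is d = 1.17. The normal approximation gives (1.960 + 1.645) × √(2/20) = 1.14. A one-sided test would need 1.06.

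**Step 2: paired t-test, 20 pairs.** Noncentrality is dz × √20 = 4.472dz, with 19 df. The 95% point is dz = 0.85. Power is 56.4% at dz = 0.5, 92.4% at 0.8 and 98.9% at 1.0.

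**Step 3: the independent test applied to correlated sides.** The d needed for 95% power, by simulation (50,000 replicates) for the independent test and from d = 0.85 × √(2(1 − ρ)) for the paired test:

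| ρ | 0 | 0.3 | 0.5 | 0.7 | 0.9 |
|---|---|---|---|---|---|
| Independent test | 1.17 | 1.09 | 1.03 | 0.96 | 0.87 |
| Paired test | 1.20 | 1.01 | 0.85 | 0.66 | 0.38 |

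The threshold of 1.17 therefore holds only at zero correlation. The sides are matched on inclination, Pell and Gregory class, flap, anaesthetic and suturing, so zero is not the obvious default.

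If 20 had been sized for a paired test at dz = 0.85 and the independent test were then run, power would be 91.1% at ρ = 0.3, 81.7% at 0.5 and 55.4% at 0.7.

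**Step 4: exclusions.** Power by number of patients analysed (independent rows at ρ = 0):

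| Assumed effect | 20 | 18 | 16 |
|---|---|---|---|
| Independent, d = 1.17 | 95.0% | 92.6% | 89.3% |
| Independent, d = 1.5 | 99.6% | 99.2% | 98.4% |
| Paired, dz = 0.85 | 95.0% | 92.5% | 88.8% |
| Paired, dz = 1.0 | 98.9% | 97.9% | 96.2% |

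The fall below 95% occurs only if 20 was just sufficient. The plan says greater than 95%, not exactly 95%.

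**Step 5: beta for moderate effects.** With the independent test, beta at d = 0.5 and 0.8 is 0.66 and 0.31 at ρ = 0, and about 0.75 and 0.20 at ρ = 0.7. These effects are chosen for illustration. The document does not say that a moderate effect was the target.

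**The case for a change.** The strongest case for a change is that the sentence is unconditional and that every threshold in Steps 1 to 3 for the named test is a large effect, from 0.87 to 1.17 SD. For a difference of 0.5 SD, correlation does not rescue that test: its power goes from about 34% at ρ = 0 to about 25% at ρ = 0.7. At 0.8 SD and ρ = 0.5 it has about 75%, against 92% for a paired test. Restating the sentence would cost little and need no more patients.

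Much of this stands. The arithmetic is right, the inputs are absent, and no allowance for the surgery-time exclusion is stated. Three things do not follow:

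- **The figure is not shown to be missed.** With no planning effect on record, a large one would satisfy it.
- **The erosion is hypothetical.** The exclusion is worded conditionally, no excluded case is reported, and in a document written in the past tense the 20 may already be the number analysed.
- **The rewrite would not supply what is missing.** A statement that 20 pairs give 95% power for 0.85 SD of the difference is worked back from 20. It is not the sponsor's rationale, and it describes a paired test that the plan does not name. Whether an independent test suits paired sides is a separate question about the analysis, which a new power sentence would not settle.

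**Conclusion.** The power statement is under-documented and cannot be verified, but the document does not show it to be false. It implies a large effect: about 1.17 SD under the named test with uncorrelated sides, 1.09 to 0.87 SD at correlations of 0.3 to 0.9, or 0.85 SD of the within-patient difference under a paired test. These values assume two-sided testing and equal SDs. Losing two to four patients would cost roughly 2 to 6 percentage points if 20 were just enough, and could leave power above 95% if the planned effect were larger.

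No change to the plan follows. The missing inputs are reporting detail. Patients attended from October to December 2017 and the document is dated November 2019, so neither the sample nor any estimate, interval or p-value would move with a new power sentence. A reader facing a null result should judge what it excludes from the confidence interval for the difference in suctioned volume, not from the planning power.

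### The planned independent t-test has neither a patient nor a side term, although the design is split-mouth and the plan itself calls the right side easier for its one surgeon

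*Combined protocol and SAP*

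**What the plan says.** The document has no numbered sections, so places are given by paragraph.

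- **Opening paragraph.** Twenty patients each have both mandibular third molars removed. On size it says only: "The sample size was defined to obtain test powers greater than 95" percent, at alpha 0.05. It gives no effect size, SD or within-patient correlation.
- **Allocation paragraph.** The right side is "easier and less time-consuming for the right-handed surgeon to extract the impacted molar on the right side", which is the reason given for using a single right-handed surgeon. On allocation: "For each patient, the control and the experimental sides were chosen by a table of random numbers". No restriction to equal numbers of warm-on-right and warm-on-left is described.
- **Surgery time paragraph.** Time is recorded: "The total time needed for surgery was measured from the moment of the LA injection until the end of suturing". There is also an exclusion without a threshold: "In case the surgery on one side took a relatively longer time, that case would have been excluded".
- **Irrigation paragraph.** Irrigation volume is equalised between sides. The plan presumes that "salivary secretion rates were almost the same between surgeries" and concludes that "the difference between the volumes of suctioned solutions were due to the differences in bleeding".
- **Final paragraph.** "Independent sample T-test were used to analyze the findings". No other test, patient term or side term is mentioned.

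**The concern.** Each patient supplies one warm and one control measurement, so the two are probably correlated. An independent-samples test treats the 40 sides as unrelated. It puts between-patient variation, which cancels within a pair, into the error term.

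The plan also names a second source of structure, side of the mouth. Using one surgeon makes the right/left difference consistent across patients but does not remove it. What the plan states is a difference in ease and time. The text does offer one route from time to the outcome: if saliva flows at an equal rate, a longer operation collects more fluid, and the plan reads any leftover volume difference as bleeding. If side does affect volume, an uneven right/left split would move the treatment estimate, the rest of the side effect would add noise, and the type I error of the planned test would shift again.

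**Working it through.** **Inputs.** From the documents: 20 pairs, alpha 0.05, power above 95%, sides drawn from a random-number table, independent t-test. Assumed, because not given: two-sided testing, all 20 pairs analysed, simple 1:1 allocation, within-patient correlation r (net of side) of 0 or 0.5, and a left-right effect on volume of 0 to 1 SD.

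**1. The plan's own figure.** The sample size cannot be reproduced without an effect size and SD. Solving backwards with the noncentral t, 20 pairs give 95% power for:
- an effect of 0.850 SD of the paired difference (paired test, 19 df): calibration A;
- an effect of 1.170 within-arm SD (independent test, 38 df): calibration B.

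**2. Missing patient term.** Let σ be the within-arm SD net of side, and n = 20. The true variance of the mean difference is 2σ²(1−r)/n; the independent test estimates 2σ²/n. At r = 0.5 its standard error is too large by a factor of √(1/0.5) = 1.41. Simulation with no side effect gives type I error 0.7%, and under A power of 82% against 95% for the paired test.

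**3. Chance imbalance.** With k of 20 patients having warm saline on the right, the estimate moves by |2k−20|/20 of the left-right difference. From Binomial(20, 0.5), P(10/10) = 17.6%.

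| Split or worse | Probability | Share of left-right difference carried |
|---|---|---|
| 13/7 | 26.3% | at least 6/20 = 0.3 |
| 14/6 | 11.5% | at least 8/20 = 0.4 |
| 15/5 | 4.1% | at least 10/20 = 0.5 |

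Either direction is equally likely, so the expected bias is zero.

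**4. Type I error with a side effect s.** Over simple allocation the true variance is [2σ²(1−r) + s²]/n, and the test estimates [2σ² + s²/2]/n. These are equal when s²/2 = 2rσ², that is s = 2σ√r, or 1.41σ at r = 0.5. Simulated type I error of the planned test for s = 0, 0.5 and 1 within-arm SD is 4.9, 5.6 and 7.2% at r = 0, and 0.7, 1.3 and 3.1% at r = 0.5.

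**5. Power (A, r = 0.5, 100,000 simulated trials per cell, simple allocation).** Side effect in SDs of the paired difference:

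| Side effect | Planned test | Paired | Paired + side |
|---|---|---|---|
| 0 | 82% | 95% | 94% |
| 0.25 | 81% | 94% | 94% |
| 0.5 | 77% | 90% | 94% |
| 1 | 66% | 72% | 94% |

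At 0.5, pairing adds 13 points and the side term 4. At 1, pairing adds 6 and the side term 22. The side term breaks even near 0.25. Under B at r = 0.5 with a 0.5 SD side effect, the three powers are 97.5, 99.3 and 99.7%.

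**6. Given the split drawn (A, r = 0.5, side effect 0.5).** At 14/6, type I error is about 2.9% for the planned test, 9.8% for an unadjusted paired test and 5.0% with the side term. Power of the unadjusted paired test is 99% or 72%, depending on which way the imbalance falls; with the side term it is 91% either way.

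**7. Cost of the side term when side has no effect.** It uses one df and multiplies the variance by 1/(1−m²), where m is the share in step 3. The standard error rises by 1/√0.91 = 1.05 at 13/7, 1/√0.84 = 1.09 at 14/6 and 1/√0.75 = 1.15 at 15/5. Power under A is 94.9% at 10/10, 92.9% at 13/7, 90.9% at 14/6 and 87.6% at 15/5. The average over simple allocation is 93.6%, against 95.0% for the unadjusted paired test.

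**The case against.** The strongest reply is that no passage links side to suctioned volume, so every side-effect figure above is conditional on an assumption. That stands. The plan also takes steps that should shrink any such effect: similar inclination and the same impaction class on both sides, matched flap, anaesthetic and suturing, equalised irrigation volume, and exclusion of cases where one side took longer. The simulations give these no credit. They remain partial, because matching teeth does not address handedness, and the exclusion has no threshold and acts after allocation.

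It is also fair that the absence of a 10/10 restriction is inferred from silence in a short document, so the imbalance probabilities rest on simple allocation. Omitting a side covariate at n = 20 would be a defensible choice in a paired analysis. And if a patient's two sides were uncorrelated and side had no effect, the planned test would do slightly better than the paired analysis with a side term (96% v 94% under A, 95% v 92% under B).

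Three stronger readings are tempting and are not supported:
- **That the result is biased by side.** Side is randomised within patient, so there is no systematic bias; only the split actually drawn can matter.
- **That side inflates the planned test's type I error.** With r = 0.5, side effects up to 1 SD bring it from 0.7% towards 5%, not above it. It exceeds 5% only when the side effect is large relative to between-patient variation, or when the sides are uncorrelated.
- **That the 9.8% at a 14/6 split describes this plan.** It belongs to an unadjusted paired test, which the plan does not use.

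None of this defends the unpaired test on split-mouth data when a patient's two sides are correlated.

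**Conclusion.** The point holds in two parts of unequal weight. The definite fault is the missing patient term. With positively correlated sides the planned test is conservative and wastes the split-mouth design, by 13 points of power under calibration A at r = 0.5. The correlation and effect size are assumed, so the size of the loss is illustrative; its direction is not in doubt for any positive correlation.

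The missing side term matters only if side affects suctioned volume, which the documents neither show nor size and which may be zero. If it does, the realised split shifts the estimate, some precision is lost and the type I error moves further. A paired analysis with a side term holds type I error at 5% whatever the split, but it gains power only if the side effect exceeds about 0.25 SD of the paired difference. With correlated sides, most of the gain comes from pairing at small to moderate side effects, and from the side term at a side effect near 1 SD. Without the right/left split and the volumes by side, a reader cannot tell which case applies. This is worth considering, with medium confidence.

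**What to change.** 1. Replace the independent t-test with an analysis of the within-patient difference in suctioned volume (control minus warm).
2. Show beside it the same analysis with a +1/−1 term for warm-on-right, or an equivalent mixed model with patient random and treatment and side fixed. Adding side to the independent test alone is not enough if the two sides are correlated.
3. Label both results as departures from the stated test made after patients were seen. Recruitment was in 2017 and the document is dated November 2019.
4. Report the right/left split by treatment, mean volume and measured surgery time by side, and the number of cases the duration exclusion removed, with the side and treatment concerned.
5. Do not adjust for surgery time: it is measured after allocation and could itself respond to the treatment.

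The pairing needs no new data. The side term needs the allocation list, if it was kept. If side has no effect, the side term costs about 1.4 points of average power (95.0 − 93.6), or about 4 points at a 14/6 split (95.0 − 90.9). That is why the unadjusted paired result should stand next to it.

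### The plan randomises which side gets which temperature but not, as far as it says, which surgery comes first, and the named t-test has no pairing, order or side term

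*Combined protocol and SAP*

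**What the plan says.** The combined protocol and SAP has no numbered sections, so places are given by topic.

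- **Design:** a split-mouth trial in which "20 patients who were candidates for bilateral surgical extractions of mandibular third molars were chosen".
- **Randomisation:** "For each patient, the control and the experimental sides were chosen by a table of random numbers". This assigns temperature to left or right within each patient.
- **Blinding:** "The surgeon was aware of the experimental side". The outcome assessor and the data analyst were blind.
- **Order:** nothing is said about which side was operated first, how that was decided, whether it was recorded, or how far apart the surgeries were. Order is not named among the variables matched between sides.
- **Measurement:** the difference in suctioned volume is attributed to bleeding, on the presumption that "salivary secretion rates were almost the same between surgeries". A further rule concerns irrigant: "In case the volume of irrigation solution was different between control and experimental sides, compensative amount of saline was poured". Its purpose was to even out the totals collected from the two sides.
- **Analysis:** "Independent sample T-test were used to analyze the findings". No pairing, order term or side term is mentioned.
- **Sample size:** "The sample size was defined to obtain test powers greater than 95"%, with no effect size, SD or within-patient correlation.

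**The concern.** In a split-mouth trial, side and order are two separate factors. The plan recognises that side matters, because it notes that the right side is quicker for this right-handed surgeon, and randomising side deals with that. Order is left open. An operator who knew the allocation could have done the control side first in every patient and still have complied with the text.

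The outcome is a raw fluid volume. A systematic difference between first and second surgery in saliva, swallowing or residual fluid would therefore enter it directly. If order went with temperature, such a difference could not be told apart from an effect of warm saline. The named test could neither reveal nor remove it, because it treats the 40 sides as two unrelated groups of 20. At stake is whether the estimated difference can be read as an effect of temperature.

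**Working it through.** **1. The plan's own figure.** The power claim cannot be reproduced, because no effect size or SD is given. Working backwards at two-sided 5% with the t distribution, 95% power with 20 patients needs a difference of 0.85 SD of the paired difference in a paired test, or 1.17 single-side SD in an independent-samples test with 20 per group. The claim is neither confirmed nor refuted, and the present point does not depend on it.

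**2. Bias.** For each patient let y = experimental minus control volume, and let s = +1 if control was done first and −1 if the experimental side was first. With treatment effect τ and order effect π (second minus first),

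y = τ + π·s + error.

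The mean of y estimates τ + π·m, where m is the mean of s over the 20 patients, so the bias is π·m.

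| Split (control first : experimental first) | m | Bias |
|---|---|---|
| 10:10 | (10 − 10)/20 = 0 | 0 |
| 14:6 | (14 − 6)/20 = 0.4 | 0.4π |
| 15:5 | (15 − 5)/20 = 0.5 | 0.5π |
| 18:2 | (18 − 2)/20 = 0.8 | 0.8π |
| 20:0 | 20/20 = 1 | π |

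**3. False-positive rate of a paired t-test.** Assumptions: τ = 0, 20 pairs, normal errors, two-sided 5%, π in SDs of the paired difference. The documents give neither π nor the split.

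At 20:0 and π = 0.5 the noncentrality is 0.5 × √20 = 2.236 on 19 degrees of freedom. Against a critical value of 2.093 the rejection probability is 0.5645. The other entries are from simulation with 200,000 replicates.

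| π | 20:0 | 18:2 | 15:5 | 10:10 |
|---|---|---|---|---|
| 0.3 | 25% | 17% | 9% | 4% |
| 0.5 | 56% | 36% | 14% | 3% |

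**4. The test that the plan names.** With within-patient correlation ρ, the SD of the paired difference is √(2(1 − ρ)) single-side SDs. An order effect of 0.5 SD of the paired difference is therefore 0.5 × √(2(1 − ρ)) single-side SDs. With control always first and τ = 0, the independent-samples t-test rejects as follows (simulation, 38 degrees of freedom).

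| Assumed ρ | Order effect (single-side SD) | Rejection rate |
|---|---|---|
| 0 | 0.71 | 59% |
| 0.5 | 0.50 | 28% |
| 0.7 | 0.39 | 10% |

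The bias, as a multiple of π, is the same as in step 2. The rate falls as ρ rises only because the test overstates the standard error when it ignores the pairing. The same feature costs power against a real effect.

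**5. If order was unrelated to allocation.** If s behaves like a fair coin, the expected bias is 0 and the unadjusted paired test rejects about 5% of the time at π = 0.3 and at π = 0.5. Chance imbalance remains: 14:6 or worse in either direction has probability 0.115, and 15:5 or worse 0.041.

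**6. Adding an order term.** When y is regressed on s, the variance of the intercept is (σ²/20) × 1/(1 − m²), where σ² is the residual variance.

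- 10:10: the factor is 1. The effect detectable with 95% power moves from 0.850 to 0.853 SD of the difference, through one lost degree of freedom.
- 15:5: 1/(1 − 0.25) = 1.33, so the standard error rises by 15%.
- 18:2: 1/(1 − 0.64) = 2.78, so the standard error rises by 67%.
- 20:0: undefined, because treatment and order are the same contrast.

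In simulation at 15:5 and 10:10, with π of 0.25, 0.5 and 0.8, the adjusted test rejected about 5% of the time.

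**The case against.** A reader might infer that order was not randomised, or that randomising side can never balance order. The documents support neither. They are silent on order, and silence does not show that order was left to choice. If the same anatomical side always went first, randomising side would also have randomised order relative to temperature, leaving only the chance imbalance of step 5. The same holds for any rule unrelated to allocation. This part of the objection stands, and it makes the point conditional.

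It is also fair to say that the paired-test rates are not those of the plan, which names a different test. They match it only when the within-patient correlation is near zero, so both sets are shown.

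Two mechanisms should not be pressed. The text does not say which side received the compensating saline, so no order-related bias can be derived from that rule. Nor does it say whether both sides were done in one session; its wording about saliva suggests separate surgeries without proving it, so carry-over from the first side to the second is conjecture.

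What remains is that nothing in the text rules out an order tied to temperature, the operator knew the allocation, and the analysis could not correct for it.

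**Conclusion.** The point holds in conditional form. Confounding of temperature with order is possible under the plan as written, but it is not demonstrated. The bias is between zero (balanced order) and the whole order effect (order always following temperature).

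For the assumed order effect of 0.5 SD of the paired difference and no true effect, the false-positive rate with control always first is about 56% for a paired test. For the planned test it is between about 10% and 59% as the assumed correlation goes from 0.7 to 0. If order was in effect random, the paired rate is about 5%. The order effect, the order split and the correlation are all assumptions.

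One part does not depend on the order history: an independent-samples t-test does not fit paired data and cannot adjust for order or side. The sponsor should make the change, but the documents do not justify calling the result biased.

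**What to change.** Patients were selected in October to December 2017, the document is dated November 1, 2019, and the text is in the past tense, so the usable remedy is retrospective.

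1. Take the order and date of each surgery from the operating records, and state how order was decided.
2. Tabulate order by treatment and by right/left side.
3. Replace the independent-samples t-test with a within-patient analysis of suctioned volume. Regress the paired difference (experimental minus control) on ±1 codes for order and for side, with the intercept as the treatment effect. If order always followed anatomical side, the two codes are identical up to sign; keep one, and the intercept can still be estimated.
4. If order nearly always followed treatment, state that the two effects cannot be separated and report this as a limitation.

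If any surgeries remain to be done, draw order from the same random-number table, balanced and crossed with side. For 20 patients that is 20/4 = 5 in each combination.

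The cost is a search of the records and two model terms, with no extra patients. The two terms take two degrees of freedom, leaving 17. With balanced order the loss of precision is negligible. With unbalanced order the order term alone raises the variance of the treatment estimate by the factors in step 6 (1.33 at 15:5 and 2.78 at 18:2), and this should be reported with the result.

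### Attributing the whole suctioned-volume difference to bleeding needs equal operating times as well as equal salivary rates, and the planned t-test uses neither recorded time nor jaw side

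*Combined protocol and SAP*

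**What the plan says.** The combined protocol and SAP has no numbered sections. All but one of the relevant statements are in the paragraphs on surgery, irrigation and suction.

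- **Outcome.** Saliva is part of the fluid collected, because "patients were asked to prevent swallowing till the end of surgery so that all the solutions and debris were suctioned from the oral cavity". Irrigation volume is equalised: where the sides differed, a "compensative amount of saline was poured into the mouth and suctioned to balance the amount of suctioned solutions". No similar step is described for saliva.
- **Attribution.** The plan presumes that "salivary secretion rates were almost the same between surgeries, so that the difference between the volumes of suctioned solutions were due to" bleeding.
- **Time by jaw side.** One surgeon performed every operation, and the plan says "it is easier and less time-consuming for the right-handed surgeon to extract the impacted molar on the right side".
- **Time safeguard.** "In case the surgery on one side took a relatively longer time, that case would have been excluded". No cut-off in minutes or percent is given.
- **Time record.** "The total time needed for surgery was measured from the moment of the LA injection until the end of suturing".
- **Allocation.** "For each patient, the control and the experimental sides were chosen by a table of random numbers". No blocking or right/left balancing is described.
- **Analysis.** An independent-sample t-test. Neither time nor jaw side is mentioned in it.
- **Size.** From the opening paragraph: "20 patients who were candidates for bilateral surgical extractions of mandibular third molars were chosen".

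**The concern.** The attribution sentence moves from a rate to a volume. Two operations with the same salivary flow give the same saliva volume only if they last the same time. The plan leaves that second condition out of the sentence, although it expects one jaw side to be quicker than the other. Any saliva difference caused by a time difference is then read as a bleeding difference.

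What is at stake depends on where the time difference lies:

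- **Between right and left.** Random allocation of the warm side makes the expected effect on the treatment comparison zero. What remains is noise and, in a single allocation of 20 patients, possible chance imbalance.
- **Between warm and control.** The saliva difference would go straight into the estimated effect.

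The plan records operating time but does not use it to tell these two cases apart.

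**Working it through.** **The plan's own figure.** There is none on this point: the documents give no salivary rate, operating time, volume or standard deviation. The stated power above 95% with 20 patients cannot be reproduced either, since no effect size or SD is given. Nothing below depends on it.

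**Step 1: saliva difference within a patient.** With equal rate r on both sides and time difference dt, the saliva difference is r x dt. It is zero only if dt = 0. Both inputs here are assumptions.

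| Assumed rate | dt = 3 min | dt = 5 min | dt = 10 min |
|---|---|---|---|
| 0.5 mL/min | 1.5 mL | 2.5 mL | 5 mL |
| 1 mL/min | 3 mL | 5 mL | 10 mL |
| 2 mL/min | 6 mL | 10 mL | 20 mL |

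**Step 2: how much reaches the treatment comparison when time differs by jaw side.** Let k of the 20 patients have the warm side on the slower jaw side. The mean warm-minus-control difference shifts by r x dt x (2k - 20)/20. Averaged over random allocations this is zero. For a given allocation:

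| Split | Share of r x dt passed on | Probability of a split this uneven or worse |
|---|---|---|
| 12:8 | 20% | 0.503 |
| 13:7 | 30% | 0.263 |
| 14:6 | 40% | 0.115 |

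An exact 10:10 split has probability 0.176. The probabilities are Binomial(20, 0.5), two-sided, and assume simple randomisation. At 13:7 the range in step 1 gives a shift of 0.30 x 1.5 = 0.45 mL to 0.30 x 20 = 6 mL.

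**Step 3: chance imbalance and added variance are one quantity.** Take a side component of +/-5 mL and an otherwise assumed SD of 10 mL for the within-patient differences. The SD becomes sqrt(100 + 25) = 11.2 mL, and the standard error of the mean goes from 10/sqrt(20) = 2.24 to 11.18/sqrt(20) = 2.50 mL. The chance shift itself has SD 5/sqrt(20) = 1.12 mL, and sqrt(2.24^2 + 1.12^2) = 2.50. So in a within-patient analysis the added variance already carries the imbalance, and the two must not be counted as separate harms. On these assumed values the precision is that of 20 x 100/125 = 16 pairs.

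**Step 4: what a side term does.** Write D = tau + beta x + error, where D is warm minus control within a patient, and x is +1 if the warm side is the right and -1 if it is the left. The intercept tau is the simple average of the two side-specific means, whatever the split. In step 3's example a 13:7 split shifts the unadjusted mean by 0.30 x 5 = 1.5 mL, and does not shift tau. The price at 13:7 is a variance of (1/4)(1/13 + 1/7) = 0.055 times the residual variance, against 1/20 = 0.050.

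**Step 5: time differing by arm.** If one arm's operations were longer by dt on average, the effect estimate would carry the full r x dt. A side term does not remove this. Only the recorded times can show whether it happened.

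**The case against.** The strongest reply is that the plan does not rest on salivary rates alone. It uses one surgeon, matches flap type, anaesthetic cartridges and suturing within each patient, requires the same Pell and Gregory class and similar inclination on both sides, describes the interval from injection to start as about the same, and excludes cases in which one side took clearly longer. The remark about the right side explains why a single surgeon was used. It gives no size and does not describe the cases left after exclusion. A reader might infer that the plan contradicts itself. That goes too far: the time safeguard exists but is undefined.

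A reader might also infer that saliva biases the comparison of warm with control. The documents do not support that. The only documented time difference is right versus left, the warm side is random, and nothing in the text says that saline temperature changes operating time.

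Third, every magnitude here comes from assumed inputs, and the exclusion rule may well have removed differences as large as 10 minutes.

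All of this stands. It limits the point to an unstated condition and an unused variable. It does not make the inference valid, because the exclusion limits the time difference without making it zero, and matching for difficulty does not remove an effect of the surgeon's handedness.

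**Conclusion.** The point holds in a limited form. Equal salivary rates do not by themselves justify assigning the whole volume difference to bleeding: similar durations are also needed. The plan relies for this on an exclusion without a threshold, and its t-test uses neither the recorded time nor the jaw side.

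The consequence of the jaw-side time difference is noise and possible chance imbalance, with zero expected bias. The 0.26 probability of a 13:7 or worse split assumes simple randomisation of 20 patients. Systematic bias would arise only if operating time differed by arm, which the documents do not address. The amount of saliva involved is unknown: 1.5 to 20 mL per patient is the product of assumed ranges, the low end could be unimportant, and the documents give no bleeding volume to set it against.

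**What to change.** 1. **Main analysis.** Replace the independent-sample t-test with an analysis of the within-patient volume difference, warm minus control, including a right/left term coded +1/-1. The coding matters: with 0/1 coding the intercept would be the effect for one side only.
2. **Reporting.** Give recorded operating time by arm and by side, and state the cut-off used for the time exclusion.
3. **Supportive sensitivity analysis.** From each side's volume subtract an assumed salivary rate times the recorded time, over a stated range such as 0.5 to 2 mL/min, and repeat the main analysis. Note that recorded time starts at the anaesthetic injection and may not match the suction period.
4. **Regression on the time difference.** Exploratory only. Time is observed after randomisation and bleeding may itself affect it, so adjustment could remove a real effect. It must not decide the conclusion.
5. **Wording.** State that the attribution assumes similar durations as well as similar salivary rates. Qualify the bleeding conclusion if times differ by arm or if the analysis in item 3 materially changes the result.

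The cost is small. The side term takes one degree of freedom from a paired analysis (18 instead of 19), and the rest is a little extra analysis. Operating time is already recorded and jaw side is known from the allocation, so no new measurement is needed. Patients attended in October to December 2017 and the document is dated November 2019, so any analysis added after the data were seen should be labelled as such.
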